1. OBJECTIVES

1.1 Study Design

This is a single-arm, two-stage phase 2 study to evaluate the response to abemaciclib monotherapy in patients with Rb-positive, triple negative metastatic breast cancer. The first stage of the study includes 13 patients with Rb-positive, triple negative metastatic breast cancer. If in the first stage there is at least one response, accrual will continue to the second stage where an additional 25 patients will be enrolled. If there are at least 4 responses among the 38 patients, the regimen would be considered to be worthy of further study.

1.2 Primary Objectives

To evaluate the efficacy of abemaciclib, as defined by objective response rate (ORR) in patients with Rb-positive triple-negative metastatic breast cancer (ORR as confirmed Complete Response (CR) or Partial Response (PR) per Response Evaluation Criteria in Solid Tumors (RECIST) Version 1.1).

1.3 Secondary objectives

1.3.1 To evaluate abemaciclib with respect to each of the following:

- 1) Progression-Free Survival (PFS)
- 2) Overall Survival (OS)
- 3) Disease control rate (DCR)
- 4) Clinical benefit rate (CBR)

To detect if there is a difference in clinical outcomes between patients with and without phospho-Rb reduction.

1.4 Exploratory objectives

To explore additional potential biomarkers in blood and tumor tissue samples that might predict response or resistance to abemaciclib.

To determine the association between genomic alterations in tumor DNA (mutations, copy number alterations, mutational burden) and RB expression and other tissue biomarkers by immunohistochemistry as well as response to abemaciclib.

To determine if there are any changes in the T-cell phenotype during exposure to abemaciclib.

To explore changes in the microbiome induced by therapy comparing stool samples collected at

baseline, during treatment, and at the time of progression. Changes in microbiome will be compared to other trial endpoints.

2. BACKGROUND

2.1 Triple-Negative Breast Cancer

Breast cancer remains a major cause of cancer death for women globally. Indeed in the USA alone, more than 39,000 women succumbed to the disease in 2013 [1]. Breast cancer is comprised of a number of different subtypes, and the triple negative subtype (TNBC) currently presents the most significant clinical challenges [2] [3]. At present, the only available systemic therapies for patients with advanced TNBC are cytotoxic chemotherapies, and there are no targeted or biologic therapies approved to treat this disease [4].

Unfortunately, there are currently no therapeutic options for patients with advanced TNBC that has progressed after several lines of cytotoxic chemotherapy. Therefore, although TNBC constitutes approximately 20% of all breast cancers, it is the cause of almost half of all breast cancer deaths. Novel approaches to treating the disease are clearly needed.

Recently there has been increasing attention on the use of cell-cycle targeting agents in the treatment of breast cancer. In particular, inhibitors of the cyclin-dependent kinases CDK4 and CDK6 (CDK4/6 inhibitors) are the subjects of great interest, due to the fact that mammary epithelial cells (particularly those of the luminal lineage) are thought to depend on these CDKs for proliferation. In keeping with this, recent trials have confirmed striking efficacy of CDK4/6 inhibitors in patients with estrogen-receptor positive breast cancers [5].

CDK4/6 inhibitors act by inhibiting the phosphorylation of the retinoblastoma tumor suppressor protein (RB). This in turn mitigates the expression of genes under the control of the E2F family of transcription factors, halting progression of tumor cells from the G1 to S phase of the cell cycle. As such, tumors that lack a functional RB protein (whether through gene deletion, mutation, or epigenetic silencing) are predicted to cycle in a CDK4/6-independent manner and thus be inert to the effects of CDK4/6 inhibition [6].

Traditionally, TNBC is associated with loss of function of RB and as such TNBC is not classically considered as a good candidate for response to CDK4/6 inhibition. However, it is clear that there is a subset of TNBC that retains intact RB protein and function. Depending on the methodology used, it is estimated that the rate of Rb loss in TNBC stands between 50-75% [6]. Therefore, there is potential that the remaining TNBC's which retain RB function may exercise cell cycling in an RB-dependent fashion, and that CDK4/6 inhibitors could be an effective treatment strategy for these tumors.

Gene expression analysis from cohorts of TNBC's have identified multiple different TNBC subtypes [7]. Notably, one subtype (the "Luminal Androgen Receptor" (LAR) subtype), shows a strong androgen receptor driven pattern of gene expression, and LAR tumors typically express RB [8]. This group includes somewhere between 10-12% of TNBCs [9]. Recently, Traina et al presented results of a phase 2 study of an androgen receptor inhibitor in patients with

AR-positive metastatic TNBC (i.e. predominantly tumors of the LAR subtype). They observed an 8% response rate and a 16-week clinical benefit rate of 35% [9]. Given that this subset of TNBCs is typically RB-positive, there is a strong biological rationale to suggest that they might be susceptible to CDK4/6 inhibition. Furthermore, recent preclinical work suggests that triple-negative cell lines of both the LAR and mesenchymal-stem like (MSL) subsets are sensitive to CDK4/6 inhibition in vitro [10]. Collectively, the LAR and MSL subtypes comprise approximately 20% of all TNBCs.

Given the rationale for determining the effects of CDK4/6 inhibitors in TNBC with intact RB function, it is important to try and determine RB functionality in TNBCs. At present, there is no standardized way to do this. Various research groups have explored RB expression and/or functionality on TNBCs in the past. One approach has been to use immunohistochemistry (IHC) to the RB protein itself. Using this method, RB is detected in approximately 30-40% of all TNBCs [11, 12], using a definition of positive as “strong nuclear staining”. Another has been to measure tumor gene expression and apply signatures of “RB loss”. Interestingly, in at least one study such a signature correlated with the presence of loss of heterozygosity (LOH) for the RB locus, but did not correlate well with the presence of RB by IHC [13].

Notwithstanding these studies, there is currently limited data to support a particular method of determining RB functionality in TNBCs, and there is even less data to suggest that one modality would best predict a response to a CDK4/6 inhibitor. Knudsen’s laboratory has shown in a small number of TNBC explants that the presence of RB by IHC correlated with sensitivity to CDK4/6 inhibition [14], and given the relative ease of this assay and the ability to apply it in real time to clinical care, this would appear to be a reasonable surrogate for RB functionality in TNBCs.

In the present study, we have elected to use immunohistochemistry to screen tumors for the presence of the Rb protein. Immunohistochemistry has the following advantages:

- RB presence by IHC has been shown to correlate with sensitivity to CDK4/6 inhibitors in TNBC pre-clinically (ref 14)
- Data describing RB-positivity rates by IHC are available from other cohorts (see above)
- The assay can be performed rapidly and reproducibly

To optimize RB staining, we have worked with [name] (pathologist, BWH), who has extensive experience in the study of RB in tumors by immunohistochemistry. We have elected to use the RB antibody clone G3-245 as this has been shown to yield reproducible, reliable RB staining in tissue sections when performed in the BWH IHC laboratory. Having selected this clone, we reviewed the RB staining characteristics (using clone G3-245) of a cohort of 180 TNBCs in a tissue microarray curated by [name] and [name] at the BIDMC, with each case being represented on the microarray in triplicate. The results of this analysis have been formally presented (Patel et al, to ASCO 2017). Tumors were divided into 4 categories: 0% of tumor cells stained; 1-10% of tumor cells stained; 10-50% of tumor cells stained; >50% of tumor cells stained. Approximately 50% of tumors showed >10% of tumor cells positively stained.

We initially chose a cutoff of >10% to define RB positivity for the following reasons:

- The percentage of RB positive tumors by IHC using this cutoff is similar to that seen in previous cohorts.
- This cut off separated tumors into two clearly distinct cohorts with statistically different rates of Androgen Receptor positivity, tumor grade, and patient age (unpublished data). These are all features reported to be more common in RB-functional tumors when compared to RB non-functional tumors.

However, after reviewing the RB-positivity rates of the first 18 patients the RB positivity rate was higher than that observed in the microarray (94% vs 50%). Two pathologists reviewed the stained sections for these cases and compared them to the initial microarray used to define RB cutoffs (Patel et al, ASCO 2017) and observed no differences in scoring techniques.

The higher than expected rate of RB-positivity in the first 18 pre-screened metastatic patients might relate to differences in the populations studied in the initial microarray and our clinical study:

- In the first 18 clinical cases, some of the archival primary tumors tested were of histologic subtypes expected to show high rates of RB expression (e.g. lobular carcinomas). Although these are typically ER-positive, patients with such cancers would still be eligible for the study as long as the most recent tumor tissue specimen from that patient had previously tested triple-negative (whether the primary in question nor a subsequent metastatic biopsy). These archival specimens, would be more likely to show Rb-expression than those in the microarray, which were all primary triple-negative ductal carcinomas.
- The microarray used to define staining cutoffs was enriched for patients with BRCA mutations, which showed a lower rate of RB expression than tumors from BRCA wild-type patients (Patel et al ASCO 2017). Indeed, the RB-positivity rate in BRCA wild-type tumors in the microarray was approximately 60 percent, rather than 50 percent as seen in the entire microarray population. Our initial 18 pre-screened patients were not enriched for BRCA mutation carriers, and might thus be expected to show a rate of RB-positivity higher than 50 percent.

The two reasons described above explain to some extent why the RB-positivity rate in our initial cohort was higher than 50 percent, as observed in the microarray. However, they are unlikely to explain the positivity rate as high as 94 percent. We thus also reviewed each case carefully to determine whether RB staining in our initial trial cohort might be “overcalling” RB-positivity. On review with pathologists ([name] and [name]), we noted of the initial 18 cases pre-screened, those with between 11-25% of tumor cells stained (i.e. in the lower range of “positive”) all showed very weak staining. Those with strong staining typically showed rates of staining of >50% of tumor cells. Given this, and the uncontrolled pre-analytic variables influencing immunohistochemical stains, we have elected to alter our definition of RB-positive from “ >10% of tumor cells staining” to “ >50% of tumor cells staining”. If this definition were applied to the initial microarray, the rate of RB positivity would be 42 percent amongst all TNBCs, and the rate in our initial cohort of 18 pre-screened patients would be 72%. Given the previously described differences in populations between the microarray and our clinical cohort, we believe that this cutoff represents a more reasonable choice to define “RB-positivity” in this

study.

Any patients enrolled on this trial prior to the RB positivity change from > 10% to > 50% being IRB approved and activated may remain on-study and continue treatment with Abemaciclib per protocol.

2.2 Abemaciclib

Abemaciclib is a selective and potent small molecule inhibitor of CDK4 and CDK6. Abemaciclib demonstrates suitable physical and pharmacokinetic (PK) properties, an acceptable toxicity profile in nonclinical species, and antitumor activity in multiple mouse models of human cancer. Abemaciclib inhibits tumor growth in multiple human xenograft models including, but not limited to, the following tumor types: 1) colorectal cancer, 2) glioblastoma multiforme, 3) acute myeloid leukemia, 4) non-small cell lung cancer, and 5) mantle cell lymphoma. The safety of abemaciclib (LY2835219) has been established in a phase 1, single-arm, dose-escalation study in adult female patients with metastatic breast cancer. The most common grade 3 adverse events (greater than 5% incidence) were neutropenia (33%), leukopenia (22%), abdominal pain (11%), diarrhea (6%) and fatigue (6%). Based on pharmacokinetic data, the recommended phase 2 dose was 200 mg po bid. Recently the results of the MONARCH-1 study were presented. In this study, women with advanced, ER-positive breast cancer that had progressed after 1 or 2 lines of systemic chemotherapy were treated with abemaciclib monotherapy. Strikingly, a 19.5% response rate was observed in this moderately pre-treated population (Dickler et al, ASCO 2016). This data suggests that abemaciclib can have meaningful clinical activity in RB-proficient tumors even in the context of chemotherapy resistance.

The present study is a two-stage single arm phase 2 study of abemaciclib monotherapy in patients with metastatic RB-positive TNBC. The investigators will perform this study in compliance with the protocol, good clinical practice (GCP) and International Conference on Harmonization (ICH) guidelines, and applicable regulatory requirements.

Formally, abemaciclib refers to the free base, whereas LSN2813542 refers to abemaciclib mesylate; however, abemaciclib has been used for uniformity throughout this protocol, except when important for experimental clarity.

More information about the known and expected benefits, risks, and reasonably anticipated adverse events (AEs) of abemaciclib may be found in the Investigator's Brochure (IB). Information on AEs expected to be related to the investigational product may be found in Section 7 (Development Core Safety Information) of the IB. Information on serious adverse events (SAEs) expected in the study population independent of drug exposure and that will be assessed by the sponsor in aggregate, periodically during the course of the study, may be found in Section 6 (Effects in Humans) of the IB.

2.3 Rationale

In cancer cells, genes that normally control the cell cycle are often dysregulated, leading to uncontrolled cellular proliferation [15]. The cyclin D-CDK4/6 holoenzyme controls G1 restriction point via phosphorylation and deactivation of RB [16].

The clinical development of CDK4/6 inhibitors in breast cancer has largely been restricted to patients with ER-positive tumors, as the majority of TNBC's is expected to lack functional RB and are thus not likely to respond to pharmacologic inhibition of CDK4/6. However, as described above a proportion of TNBCs are RB-proficient and in preclinical models have been shown to respond to CDK4/6 inhibition. The present study aims to determine the clinical efficacy and tolerability of abemaciclib in patients with RB-positive, advanced TNBC.

2.4 Correlative Studies Background

In this study, correlative scientific aims will be addressed by performing analysis of both archival patient specimens and specimens obtained during the course of the study. The overarching goal of these studies is to explore possible predictors of response to abemaciclib amongst RB-positive TNBC's. Furthermore, studies will seek evidence of a pharmacodynamic response to abemaciclib therapy (through a tumor biopsy obtained on study) to determine if this correlates with response to therapy.

The main candidate biomarker of tumor sensitivity to CDK4/6 inhibitors is the presence of intact, functional Rb [6]. At the time of screening patients for eligibility, therefore, we will perform immunohistochemistry to identify RB status on archival tumor tissue. Only patients that are RB-positive (greater than 50% of tumor cells staining positive) will be eligible for the study.

Other than RB, there are no validated biomarkers for predicting response/resistance to CDK4/6 inhibitors in breast cancer. Candidate markers of response include amplification of cyclin D1 and loss of the CDK4/6 inhibitor p16 [5], which are thought to render tumors more dependent on the CDK4/6 pathway. Conversely, possible predictors of resistance include amplification of cyclin E1/E2, overexpression of cyclin E, mutations in TP53, and heightened activity of phosphoinositide-dependent kinase 1. Finally, a failure of CDK4/6 inhibition to adequately achieve suppression of RB-phosphorylation, even in the presence of intact RB, is also predicted to be associated with a lack of response to therapy.

In this study, patients with biopsy-accessible disease will be required to undergo tumor biopsy prior to initiating therapy. In addition, patients will undergo a second biopsy after completion of 1 cycle (28 days) of abemaciclib therapy. Analysis of pre-treatment biopsies (or archival tissue when pre-treatment biopsies are not available) will be performed to determine correlations with the predictive biomarkers listed above (and others) and response. Comparison of RB phosphorylation between baseline and C2D1 biopsies will be used to seek evidence of pharmacodynamic effect and explore its association with response. We will also perform exploratory genomic studies (whole exome sequencing) on the tumor tissue, as well as studies on fresh tumor tissue obtained at baseline aimed at determining therapeutic combinations that enhance the effects of CDK4/6 inhibitors in TNBC.

Whole blood will be collected at the time of study entry for circulating tumor DNA (ctDNA).

From this sample, ctDNA will undergo whole exome sequencing (WES) in exploratory genomic studies to determine novel predictors of response to abemaciclib in TNBC. Further details of all correlative studies are provided in section 9 of the protocol.

The primary goal of this study is to determine the clinical efficacy of abemaciclib monotherapy in patients with advanced, “RB-positive” triple-negative breast cancer. For the purposes of the trial, we have defined RB positivity using an immunohistochemical assay – tumors in which greater than 50% of tumor cells stain positive for RB are deemed positive. In addition, to IHC, another important method for assessing RB function is through sequencing of DNA. Triple-negative tumors can often harbor either mutations or deletions in RB1, which confer a loss of RB functionality. Thus, we also wish to determine whether RB1 alterations at a genomic level might predict the response of triple-negative breast cancers to abemaciclib. In order to do this, we will access DNA sequencing data (where possible) on tumors from all patients who participate in the pre-screening process. For the majority of these patients, DNA sequencing will have already been performed using the Dana-Farber Cancer Institute’s “Profile” targeted sequencing panel, as patients who sign consent for pre-screening in this study often also sign consent for other studies through which Profile testing is performed. Here, we propose to use this data to determine the impact of RB1 genomic alterations on response to abemaciclib, and also to explore correlations between RB1 genomic alterations and loss of RB staining on immunohistochemistry.

Moreover, recent studies have implicated other genomic alterations which may also confer resistance to abemaciclib (for example, in TP53, PIK3CA, PTEN, and other genes) [20]. As such, we will also interrogate the Profile data these and other genomic alterations, as an exploratory analysis to determine genomic correlates of response to abemaciclib.

Finally, recent data has suggested that CDK4/6 inhibitors can enhance anti-tumor immune responses not only through their effects on tumor cells, but also through direct effects on effector T lymphocytes (Deng, *Cancer Discovery* 2017; Schaer, *Cell Reports* 2018). As a result, we will also collect peripheral blood mononuclear cells from patients on study, with the intent of interrogating changes in T cell phenotype with abemaciclib therapy.

The gut microbiota has been recognized as a modulator of immune system development. Healthy individuals have microbial populations in their intestinal tract that vary markedly in composition. The diversity of intestinal microbiota represents a significant challenge to the host’s immune defenses, which must balance immune tolerance of beneficial microbes with inflammatory responses against pathogens. Alterations in the gut microbiota and their resulting interactions with intestinal epithelium and the host immune system are associated with many disease, including cancer. In addition, the identification of bacterial species associated with response could open new strategies to maximize the clinical benefit of cancer therapy through the modulation of gut microbiota.

3. PARTICIPANT SELECTION

3.1 Inclusion Criteria

- 3.1.1 Patients must have histologically or cytologically confirmed invasive breast cancer, which is recurrent, locally advanced, unresectable or metastatic.
- 3.1.2 Patients must have at least one lesion that is not within a previously radiated field and that is measurable per RECIST version 1.1. Bone lesions are not considered measurable.
- 3.1.3 Either the primary tumor and/or metastatic tumor must be triple-negative as defined below:
- Hormone receptor status: the invasive tumor must be ER- and PR-negative, or staining present in <1% by immunohistochemistry (IHC)
 - HER2 status: the invasive tumor must be Human Epidermal Growth Factor Receptor 2 Negative (HER2-negative) by the ASCO CAP guidelines

In cases where both primary tumor and metastatic sample(s) have been tested for ER, PR, and HER2, then the triple-negative status of the tumor should be determined from the most recent sample available.

- 3.1.4 Either the primary tumor and/or the metastatic tumor must be RB positive as defined below:
- RB status: the invasive tumor must have greater than 50% of tumor cells staining positive for RB.
- 3.1.5 Prior Chemotherapy:
- Patients may have received 1-3 prior systemic therapies for metastatic disease (note: for patients who have first developed recurrent/metastatic disease within 12 months of completing any (neo)-adjuvant therapy for triple-negative breast cancer, the (neo)-adjuvant therapy is counted as a prior line of therapy).
 - Patients must have been off treatment with myelosuppressive chemotherapy for at least 21 days or nonmyelosuppressive agents for 14 days before registration. Patients should also be adequately recovered (to baseline or grade 1) from acute toxicities of prior treatment except for residual alopecia and peripheral neuropathy.

- 3.1.6 Prior biologic therapy: Patients must have discontinued all biologic therapy at least 21 days before registration.
- 3.1.7 Prior radiation therapy: Patients may have received prior radiation therapy in either the metastatic or early-stage setting. Radiation therapy must be completed at least 7 days prior to study registration.
- 3.1.8 Patients on bisphosphonates or RANK-L inhibitors may continue receiving these therapies during study treatment. There is no washout period required between the last dose of these therapies and the start of abemaciclib.
- 3.1.9 The patient has an Eastern Cooperative Oncology Group (ECOG) performance status 0-1 (ECOG scale provided as Appendix A)
- 3.1.10 Patients must have normal organ and marrow function as defined below:
- Absolute neutrophil count $\geq 1500/\text{mm}^3$
 - Platelets $\geq 100,000/\text{mm}^3$
 - Hemoglobin ≥ 8 g/dL
- Note:* Patients may receive erythrocyte transfusions to achieve this hemoglobin level at the discretion of the investigator. Initial treatment must not begin earlier than the day the after the erythrocyte infusion
- Total Bilirubin ≤ 1.5 x the upper limit of normal (ULN) or ≤ 2.0 x the upper limit of normal (ULN) in patients with documented Gilbert's syndrome.
 - Serum creatinine ≤ 1.5 mg/dL OR calculated GFR ≥ 60 mL/min
 - Alanine aminotransferase (ALT) and aspartate aminotransferase (AST) ≤ 3 times the upper limit of normal. For patients with documented liver metastases, AST/ALT ≤ 5.0 times the upper limit of normal.
- 3.1.11 Female subjects of childbearing potential must have a negative serum pregnancy test at screening. Women of childbearing potential are defined as those who have not been surgically sterilized and have had a menstrual period in the past year

- 3.1.12 The patient must be ≥ 18 years old
- 3.1.13 Capable of understanding and complying with the protocol and has signed the informed consent document.
- 3.1.14 Able to swallow study drug.
- 3.1.15 Sexually active patients (male and female) must use medically acceptable methods of contraception during the course of the study and for 3 months after completion of study treatment. If a woman becomes pregnant or suspects she is pregnant while participating in this study, she should inform her treating physician immediately. While on the study and for 3 months after final drug administration, women may not breast-feed.
- 3.1.16 Confirmed availability of formalin-fixed, paraffin-embedded (FFPE) tumor tissue
- 3.1.17 Patients with tumor that is felt to be accessible to biopsy must be willing to provide tissue from a newly obtained core biopsy of a tumor lesion at baseline. Biopsies will be obtained up to 1 week (7 days) prior to initiation of treatment on Cycle 1, Day 1. Patients who undergo an attempted research biopsy procedure for the purpose of this protocol, and in whom inadequate tissue is obtained, are not required to undergo a repeat biopsy in order to continue on protocol.

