3.2 Exclusion Criteria

A patient will be excluded from the study if he or she meets **any** of the following criteria:

- 3.2.1 Received a prior CDK4/6 inhibitor.
- 3.2.2 Undergone major surgery within 14 days of the initial dose of study drug
- 3.2.3 Received another investigational agent (defined as any agent/device that has not received regulatory approval for any indication) within 14 days of the first dose of study drug for a nonmyelosuppressive agent, or 21 days of the first dose of study drug for a myelosuppressive agent.
- 3.2.4 Has any severe concurrent disease, infection, or comorbid condition that renders the patient inappropriate for enrollment in the opinion of the investigator.
- 3.2.5 Has an active bacterial infection (requiring IV antibiotics at the time of initiating study treatment), fungal infection, or detectable viral infection. Patients with known HIV infection are excluded given the potential for interactions between antiretroviral agents and abemaciclib, and the potential for increased risk of life-threatening infection with therapy that is myelosuppressive. Patients with known Hepatitis B or Hepatitis C infection are excluded only if there is evidence of active infection (detectable Hepatitis B surface antigen, detectable Hepatitis C RNA)
- 3.2.6 Documented brain metastases that are untreated, symptomatic, or require therapy to control symptoms. Participants with previously diagnosed brain metastases are eligible if they have completed treatment at least 7 days prior to trial registration, are neurologically stable, and have recovered from effects of radiotherapy or surgery.
 - Any corticosteroid use for brain metastases must have been discontinued without the subsequent appearance of symptoms for ≥ 2 weeks before the first study drug.
 - Treatment for brain metastases may have included whole brain radiotherapy, radiosurgery, or a combination as was deemed appropriate by the treating physician.
 - Patients who meet the above criteria and are clinically stable on anti-convulsant medication are eligible only if their anti-convulsant does not alter hepatic cytochrome P450 activity in a way that might interfere with metabolism of abemaciclib (see Appendix C).
- 3.2.7 Pregnant women are excluded from this study because of the potential for teratogenic effects.
- 3.2.8 Lactating women are excluding from the study.

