10. STUDY CALENDAR

Baseline evaluations are to be completed within 28 days prior to registration unless otherwise specified. Laboratory assessments, including pregnancy test, are to be completed within 14 days of registration. In the event that the participant's condition is deteriorating, laboratory evaluations should be repeated within 48 hours prior to initiation of the next cycle of therapy.

Assessments must be performed prior to administration of any study agent. Study assessments and agents should be administered within ± 3 days of the protocol-specified date, unless otherwise noted. Tumor assessments must be completed within ± 7 days of the protocol-specified date.

	Screening	Cycle 1		Cycle 2		Cycle 3	Cycle 4+		30 Day FUV ^k	Follow -Up
		D1	D15	D1	D28	D1	D1	D28		
Informed consent	X									
Demographics	X									
Medical history, including past lines of therapy	X									
Physical exam	X	X	X	X		X	X		X	
Vital signs ^a	X	X	X	X		X	X		X	
Height	X									
Weight	X	X		X		X	X		X	
Performance status	X	X		X		X	X		X	
Concurrent Meds	X	X	X	X		X	X		X	
AE Evaluation	X	X	X	X		X	X		X	
CBC w/diff ^f	X	X	X	X		X	X		X	
Serum chemistry ^b	X	X	X	X		X	X		X	
Serum cystatin C ^c	X	X	X	X		X	X		X	
B-HCG	X ^d									
Blood for ctDNA ^e		X				X			X	
Blood for genomic sequencing control		X								
Blood for plasma exosome analysis ^f		X	X	X		X			X	
Blood for germline DNA ^g		X								
Blood for PBMCs	X			X		X			X	
Archival tumor tissue	X									
Research stool collection and questionnaire ^m	X					X	X		X	
Research Biopsy	X			X						
EKG ^h	X									
Tumor assessments ⁱ	X				X			X	X ^{j,k}	
Abemaciclib		X-----X								
Survival Follow-up										X

Abemaciclib: 200mg po bid for 28 day cycles.

- a. Vital signs to include: diastolic and systolic blood pressure, heart rate and temperature
- b. Chemistry to include: Albumin, alkaline phosphatase, total bilirubin, bicarbonate, BUN, calcium, chloride, creatinine, glucose, potassium, total protein, SGOT [AST], SGPT [ALT], sodium.
- c. Cystatin C should be performed each time serum chemistries are performed, as abemaciclib is known to compete for tubular secretion of creatinine, causing an increase in serum creatinine which does not reflect changes in renal function. Cystatin C allows for more accurate assessment of renal function in this context.
- d. Serum pregnancy test (women of childbearing potential as defined in the eligibility section)

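### Section 3.1.11 classes any unsterilized woman with a full year of amenorrhea as not of childbearing potential whatever the cause, so treatment-related amenorrhea at premenopausal age removes the only mandated pregnancy test

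*Combined protocol and SAP*

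**What the plan says.** All references are to the combined protocol and SAP.

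- **Who is tested.** Section 3.1.11 makes a negative serum pregnancy test at screening a condition of entry, but only for women of childbearing potential: "Women of childbearing potential are defined as those who have not been surgically sterilized and have had a menstrual period in the past year". The two conditions are joined by "and".
- **When.** The study calendar (Section 10) marks the B-HCG test in the screening column only, to be done within 14 days of registration. Footnote d limits it to the same group: "Serum pregnancy test (women of childbearing potential as defined in the eligibility section".
- **Why pregnancy matters.** Section 3.2.7 states: "Pregnant women are excluded from this study because of the potential for teratogenic effects". It attaches no test of its own.
- **Who can enter.** Section 3.1.12: "The patient must be ≥ 18 years old". Section 3.1.5: "Patients may have received 1-3 prior systemic therapies for metastatic disease". Section 2.1 says that "the only available systemic therapies for patients with advanced TNBC are cytotoxic chemotherapies". Section 3.1.5 also sets only a short washout: "Patients must have been off treatment with myelosuppressive chemotherapy for at least 21 days or nonmyelosuppressive agents for 14 days before registration".
- **Contraception.** Section 3.1.15 says that sexually active patients of either sex "must use medically acceptable methods of contraception during the course of the study" and for 3 months afterwards. It is not restricted to women of childbearing potential.

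**The concern.** A year without periods is a sensible marker of natural menopause. It is a weaker marker in women who have recently had chemotherapy or other drugs that can stop menstruation, and this trial recruits such women from age 18. For them the definition treats a side effect of treatment as if it were menopause.

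The consequence is specific. A site that follows Section 3.1.11 exactly may leave such a woman untested, and her pregnancy status before the first dose then rests on history, examination and the investigator's judgment. If a pregnancy were missed, the fetus would be exposed to a drug that the protocol itself treats as potentially teratogenic. That would be rare but serious. The matter is one of participant safety: the response-rate endpoint, the two-stage decision rule and the planned analyses are unaffected.

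**Working it through.** The plan states no figure on this point, so there is none to reproduce. The check applies the written rule to each kind of patient and then looks for any other test that would catch the ones it leaves out.

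**Step 1. The rule.** Childbearing potential = (not sterilized) AND (period within the past year). A serum test is mandated only if both are true.

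| Woman | Not sterilized | Period in past year | Mandated tests |
|---|---|---|---|
| Surgically sterilized | No | Either | 0 |
| Unsterilized, still menstruating | Yes | Yes | 1 |
| Unsterilized, treatment-related amenorrhea of under a year | Yes | Yes | 1 |
| Unsterilized, natural menopause, no period for a year or more | Yes | No | 0 |
| Unsterilized, premenopausal age, treatment-related amenorrhea of a year or more | Yes | No | 0 |

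The last two rows are treated alike because the rule contains no age limit, hormone criterion or question about cause. The fourth row is a reasonable exemption. The fifth is the gap.

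**Step 2. Is there a test elsewhere?** Section 5.2 lists the blood work for day 1 of cycle 1 and of later cycles: blood count, liver function, urea, electrolytes and creatinine. No pregnancy test is among them. The calendar has no B-HCG entry after screening. Section 3.2.7 names none, and Section 4.1 has the investigator confirm eligibility against the written criteria. The screening test in Section 3.1.11 is therefore the only mandated one.

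**Step 3. Is the fifth row foreseeable here?** Sections 3.1.12 and 3.1.5 admit adult women of any age with prior systemic therapy for advanced disease, which Section 2.1 describes as cytotoxic. Section 2.1 also explains that a patient whose earlier tumor was of a typically ER-positive histology can qualify if her most recent sample is triple-negative, so earlier hormonal treatment is possible too (an inference; the protocol does not say it). The protocol gives no ages, menstrual histories or rates of amenorrhea.

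**Step 4. Do the other provisions close the gap?** Contraception under Section 3.1.15 lowers the chance of conceiving on study but cannot reveal a pregnancy already present at entry. Medical history at screening and physical examination at screening and on day 1 of cycle 1 may raise suspicion, but they are not a pregnancy test, and a missed period cannot serve as a warning in a woman who already has none.

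**The case against.** The strongest reply is that the decisive premise is not in the documents. If a year of treatment-related amenorrhea always meant permanent loss of fertility, the exemption would be harmless. The protocol says nothing on how often such amenorrhea occurs or how often fertility survives it. This stands as a limit: the premise is an assumption, and no rate can be attached to it.

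The second reply is that the gap is narrow and other protection remains. For harm to follow, a woman must be of premenopausal age, unsterilized, amenorrheic for the whole year, still fertile, already pregnant at entry and missed clinically. Shorter amenorrhea still leads to a test. Every pregnant woman is excluded whatever her label, contraception applies to all sexually active patients, women are told to report a suspected pregnancy, and investigators may always test. All of this stands and keeps the point minor. It does not supply a test for the woman left out.

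Third, a remedy that tested every woman whose periods ended with treatment would be too broad. A woman of 65 whose periods stopped with chemotherapy years earlier has no need of a test. That is right, and the wording proposed below exempts her.

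A reader might also infer more than the text supports:

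- **That the size of the risk can be computed.** Setting the 21-day chemotherapy washout against the one-year look-back measures possible overlap with treatment. It does not measure amenorrhea, retained fertility or missed pregnancy. Total accrual is no estimate either, since it includes men and women who are sterilized, naturally postmenopausal or still menstruating.
- **That the protocol contradicts itself or admits pregnant women.** It does neither. Sections 3.1.11 and 3.2.7 and footnote d are mutually consistent. The test simply does not reach everyone to whom the exclusion applies.

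**Conclusion.** The concern holds as a minor safety point. The reading of the text is firm: an unsterilized woman with no period for a year has 0 mandated pregnancy tests, against 1 for an unsterilized woman who has had a period, and the reason for the amenorrhea plays no part. That this matters for women with treatment-related amenorrhea rests on the assumption that such amenorrhea does not always end fertility. If it always did, nothing would be lost; if it sometimes does not, the exclusion of pregnancy in those women has no objective check. How many enrolled women would fall in this group cannot be derived from the documents. It may be none and is probably few. No endpoint, sample size or analysis depends on it.

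**What to change.** Reword the definition in Section 3.1.11 so that an unsterilized woman counts as not of childbearing potential only if she has had 12 or more months without periods **and** at least one of these holds:

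1. there is no chemotherapy, hormonal or other medical cause for the amenorrhea;
2. she is clearly past reproductive age, by a fixed cut-off that the sponsor sets (60, for example; this value is an assumption, not taken from the documents);
3. she was postmenopausal before her systemic therapy began.

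All other unsterilized women, including those in whom the cause is uncertain, have the screening serum test. Footnote d needs no edit because it refers back to the eligibility definition.

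Under this wording the woman in the last row of the table is tested, unless she was postmenopausal before treatment or is over the age limit. Natural menopause stays exempt.

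The cost is one amended definition and a small number of added serum assays, run with the screening laboratory work already scheduled, so no extra visit is needed. The drawbacks are a few unnecessary tests and some judgment about why periods stopped. The rule to test when in doubt keeps that judgment from reopening the gap.
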